6.2.5 Study Completion Evaluations

For Step 2, week 72 \pm 28-days will be the final study visit for all participants, independent of the entry week for Step 2.

For participants who do not enter Step 2, the final study visit will be the last visit they had on Step 1, regardless of when that occurred.

6.2.6 Event-Driven Evaluations

Step 1: Unplanned Study Visits

Unplanned study visits should not occur after week 22 on Step 1.

The purpose of unplanned visits, should they occur, is to address common toxicities. Participants will be provided with a telephone number that they can call if they are having any problems (e.g., headache, fever, nausea, etc.) during the study treatment period (day 0 through week 12). Participants will be connected to the study staff who will talk to them and try to resolve the issue over the phone, whenever possible. Only if the study staff feels further investigations are required to resolve the complaint, an unplanned study visit should be scheduled within 5 days with the participant so that additional investigations, as deemed appropriate by the study staff, may be performed. It is possible no tests are ordered or tests not included in the SOE are ordered; however, while the protocol does not

require any testing to be performed at these unplanned visits, if any laboratory test is ordered (e.g., safety labs), a plasma specimen should be stored.

NOTE: If any laboratory, radiology, or other tests are ordered, they should be justified by medical need. Labs drawn for safety purposes are permitted. Any tests ordered are not meant to serve as an early indicator of a participant's HCV treatment response. The performance of HCV RNA testing at unplanned study visits is strongly discouraged and should be discussed with the core team. The purpose of these unplanned visits, should they occur, is to deal with common toxicities.

If a participant provides information about study treatment disposition, use (or change in use) of reportable concomitant medications, or gives information about reportable adverse events (e.g., AEs leading to change in study treatment regardless of severity grade) at this unplanned study visit, then this information should be captured on the appropriate eCRFs.

Participants who become pregnant while on study medications or up to week 22 should contact the site to schedule an unplanned study visit (see section 8.3 for details).

6.2.7 Discontinuation

Evaluations for Participants Who Do Not Start Study Treatment

All eCRFs must be keyed for the period up to and including the entry visit.

Premature Treatment Discontinuation

Participants who plan or who have discontinued their study medication prior to completing the full 84-day course will have been instructed to contact the site to alert them of premature discontinuation. The site staff will not be aware of any treatment discontinuations unless the participants inform the site. These participants will be encouraged, like all other participants, to return for their SVR evaluation visit at week 24 and remain on the study through study completion. No adjustments to the timing of the SVR evaluation will be made for premature treatment discontinuation. Participants will be provided a number to call or send a text message informing the site of the stop date.

6.3 Instructions for Evaluations

All clinical and laboratory information required by this protocol is to be present in the source documents. Sites must refer to the Source Document Guidelines on the DAIDS website for information about what must be included in the source document: <https://www.niaid.nih.gov/sites/default/files/documents/sourcedocappndx.pdf>.

All stated evaluations are to be recorded on the eCRF unless otherwise specified. Refer to section 7.0 for information on the DAIDS AE Grading Table and AE reporting of AE requirements.

6.3.1 Documentation of Active HCV Infection

Positive for HCV RNA >1000 IU/mL prior to study entry.

Section 4.1.3 specifies assay requirements for HCV documentation. HCV documentation is not recorded on the eCRF.

6.3.2 Documentation of HIV-1 Status

Section 4.1.6 specifies assay requirements for HIV-1 documentation. HIV-1 documentation is not recorded on the eCRF.

6.3.3 Calculated FIBROSIS-4 (FIB-4) Score

Calculated FIB-4 score is needed to determine cirrhosis status for all participants, as per the SOE, in order to evaluate other outcomes such as regression of liver disease.

This calculation requires the following data: Participant age (years), serum alanine and aspartate aminotransferase level (U/L), and platelet count ($10^9/L$).

Please refer to the A5360 PSWP for the website link to calculate the FIB-4 score.

6.3.4 Model for End-Stage Liver Disease (MELD) Score

The MELD score measures the mortality risk in participants with end-stage liver disease. It is used as a disease severity index to help prioritize allocation of organs for transplant. In order to calculate the MELD score, total bilirubin (mg/dl), sodium (mEq/L), INR, and serum creatinine (mg/dl) values are needed.

Please refer to the A5360 PSWP for the website link to calculate the MELD score.

6.3.5 Documentation of Cirrhosis Status

Participants with calculated FIB-4 score of <3.25 are considered to be non-cirrhotic.

Participants with calculated FIB-4 score ≥ 3.25 are considered to have cirrhosis and must have a calculated CTP score of ≤ 6 (CTP A) to be considered a compensated cirrhotic. See section 6.3.6.

6.3.6 Calculated Child-Turcotte-Pugh (CTP) Score

Calculated CTP score is needed only for participants who are considered cirrhotics as determined by the FIB-4 score (≥ 3.25) as per the SOE. CTP score must be ≤ 6 corresponding to Class A to be included in the study.

This calculation requires the following data: total bilirubin (mg/dl), albumin (g/dl), INR, evaluation for ascites (absent, slight, or moderate), evaluation for hepatic encephalopathy as per West Haven criteria (none, mild to moderate [Grade 1-2], severe [Grade 3-4]).

Please refer to the A5360 PSWP for the website link to calculate the CTP score.

6.3.7 Liver Elastography

If available, liver elastography measurement will be captured at entry visit. Liver elastography data/values from the previous 3 years will be accepted. This will not be required for study entry. Where available, liver elastography will be repeated per the SOE. See A5360 MOPS for a list of liver elastography methods.

6.3.8 Medical History

The medical history must include all signs and symptoms regardless of grade and all diagnoses identified by the ACTG criteria for clinical events and other diagnoses regardless of grade within 30 days prior to entry. In addition, the following diagnoses should be reported regardless of when the diagnosis was made:

- AIDS-defining conditions (only for HIV-1 co-infected participants)
- Bone fractures (verbal history accepted)
- Coronary heart disease
- Cancer (exclusive of basal/squamous cell skin cancer)
- Diabetes
- Tuberculosis
- Chronic HCV (If available, appropriate documentation from medical records of chronic HCV-infection, defined as having a documented HCV-positive antibody serology for greater than 6 months.)
- Chronic HBV
- Substance use (injection, non-injection drugs, and alcohol) captured via the WHO ASSIST instrument

Any allergies to any medications and their formulations must also be documented.

6.3.9 Medication History

A medication history must be present, including start and stop dates.

Table 6.3.9-1 Required Medication History

Medication Category	Complete History or Timeframe
Antiretroviral therapy	Within 90 days before study entry
Prescription drugs for treatment of opportunistic infections	Within 35 days before study entry
Prescription drugs for prophylaxis of opportunistic infections	Within 35 days before study entry
Prescription drugs (other)	Within 35 days before study entry
Non-prescription drugs	Within 35 days before study entry
Acid suppressing medications such as proton pump inhibitors (PPIs) and/or H2 inhibitors	Within 35 days before study entry
Vaccinations	Within 35 days before study entry
Sex-hormone medications or sex-hormone analogues or antagonists*	Last 12 months except as noted below

*Includes: hormone-releasing IUDs (e.g., Mirena inserted in the last 5 years); oral, injectable, implanted, or patch contraceptives; vaginal ring, creams, or inserts; estrogen, progesterone, or testosterone therapy; leuprolide or other synthetic gonadotropin-releasing hormone; tamoxifen, raloxifene, aromatase inhibitors or any other androgen, estrogen, or progesterone analogue or antagonist therapy.

6.3.10 Clinical Assessments

Complete Physical Exam

A complete physical examination must be performed at screening and is to include at a minimum an examination of the skin, head, mouth, and neck; auscultation of the chest; cardiac exam; abdominal exam; and examination of the lower extremities for edema. The complete physical exam will also include signs and symptoms, diagnoses, and vital signs (height, weight, temperature, pulse, respiration rate, and blood pressure).

Targeted Physical Exam

A targeted physical examination should be performed at entry, week 24/SVR evaluation visit and weeks 48 and 72, and should include vital signs (weight, temperature, pulse, respiration rate, and blood pressure), and is to be driven by any previously identified or new AE/targeted condition (as described in below bullets), that the participant has experienced within 14 days prior to study entry/since the last visit or at this visit.

Post entry, record the following targeted events regardless of grade:

- Uterine pregnancy
- AIDS-defining conditions (refer to the CDC HIV Classification and the WHO Staging System for HIV Infection and Disease)
- Tuberculosis
- Chronic HBV
- Ascites
- Hepatic Encephalopathy

Refer to section 7.2 for AE collection requirements.

Height

Height (in cm) will be collected once at study screening.

Weight

Weight (in kg) will be collected at study screening, entry, week 24/SVR evaluation visit, and weeks 48 and 72.

Concomitant Medications

At entry and at the week 24/SVR evaluation visit, new and discontinued concomitant medications should be recorded on the eCRFs. See section 5.4 for concomitant medications.

Study Treatment (Intervention) Modifications

When the participant takes the last tablet of each bottle of SOF/VEL, they will be instructed to contact the site to report the treatment stop date. This information self-reported by the participant should be captured on the eCRF when reported outside of and during the week 24/SVR evaluation visit. See A5360 MOPS for additional details.

At the week 24/SVR evaluation visit, record all study drug modifications, including participant-initiated modifications, inadvertent and deliberate interruptions of more than 7 days. Record permanent discontinuation of study treatment (see section 6.2.7).

6.3.11 Laboratory Evaluations

At screening and entry, all laboratory values must be recorded on the eCRF. For post-entry assessments, all laboratory values for hemoglobin, AST, ALT, blood urea nitrogen (BUN), serum creatinine, total bilirubin, sodium, INR, albumin, and platelets regardless of grade must be recorded on an eCRF. Additional reporting of abnormal laboratory findings should be performed as per requirements in section 7.2.

Hematology

Hemoglobin, hematocrit, red blood cells (RBC), white blood cell (WBC) count,

platelets.

Liver Function Tests

AST (SGOT), ALT (SGPT), total bilirubin and albumin.

Blood Chemistries

Serum creatinine, sodium, BUN

Creatinine Clearance (CrCl)

CrCl will be calculated throughout the study using Cockcroft-Gault method. Refer to the Cockcroft-Gault calculator located on the FSTRF web site. (Please refer to the A5360 PSWP for the website link to calculate CrCl using the Cockcroft-Gault calculator.)

International Normalized Ratio (INR)

This will be performed at a local laboratory.

Pregnancy Test

For women with reproductive potential: Serum or urine β -HCG. (Urine test must have a sensitivity of <25 mIU/mL.) Record pregnancy and pregnancy outcome per section 8.0.

HBV Panel

A HBV panel that includes hepatitis B surface antibody (HBsAb), hepatitis B core antibody total or IgG (HBcAb), and HBsAg will be performed during screening. HBV infection status must be confirmed prior to study entry. The panel must be performed at a laboratory that possesses Clinical Laboratory Improvement Amendments (CLIA) certification or its equivalent or at a DAIDS approved laboratory.

Results must be recorded on an eCRF.

NOTE: Active HBV infection is defined by the presence of hepatitis B surface antigen in serum (HBsAg+) at screening.

Table 6.3.11-1 Enrollment Eligibility Based on HBV Panel Results

HBsAg	HBsAb	HBcAb total or IgG	Status
Positive	Negative	Positive	Active HBV infection; NOT ELIGIBLE
Negative	Positive	Positive	Prior HBV infection with immunity; ELIGIBLE
Negative	Positive	Negative	Prior vaccination with immunity; ELIGIBLE
Negative	Negative	Positive	Isolated Hepatitis B core antibody. Prior HBV infection without immunity; ELIGIBLE

6.3.12 Immunologic Studies (For HIV co-infected participants)

CD4+

Obtain absolute CD4+ count within 90 days prior to entry from a laboratory that possesses a CLIA certification or equivalent.

6.3.13 Virologic Studies

Plasma HIV-1 RNA (For HIV Co-infected Participants)

Screening HIV-1 RNA must be performed within 90 days prior to study entry by a laboratory that possesses a CLIA certification or equivalent.

HCV RNA

Screening HCV RNA by PCR must be obtained by any FDA-approved test for quantifying HCV RNA at any local laboratory that has a CLIA certification or its equivalent. If no historical documentation is available, the screening HCV RNA must be obtained within 35 days prior to study entry.

All other samples will be collected per SOE. Only samples from participants who have achieved SVR will be collected at weeks 48 and 72 and tested for the presence of HCV RNA.

HCV RNA samples on study will be processed and shipped to the designated A5360 VSL for real-time quantitative HCV RNA analysis.

6.3.14 Stored Plasma/PBMCs/Serum

Stored plasma, PBMCs, and serum will be collected at the indicated visits for future HCV/HIV studies and shipped according to the A5360 Laboratory Processing Chart (LPC). Stored specimens will be used after study completion for HCV genotyping/sequencing to assess re-infection versus relapse and estimate SVR by genotype.

Further, the NS5A and NS5B regions of HCV will be sequenced for the earliest sample where HCV RNA is detected post-SVR and the corresponding entry sample will also be sequenced. Sequence data will assist in discriminating between reinfection (entry and post-SVR sequences are not related) versus relapse (entry and post-SVR sequences are identical). Incidence of reinfection will be calculated following the completion of sequencing.

Those who do not achieve SVR (SVR non-responders) will have both baseline and SVR specimens tested for HCV RASs by sequencing the NS5A and NS5B regions.

Any specimens collected during unplanned visits will be stored. See section 6.2.6.

6.3.15 Questionnaires

Adherence Assessment

Adherence will be captured at the week 4 remote contact (see section 6.3.22) and week 24/SVR evaluation visit (i.e., week 22 or beyond). At both assessments, participants will be asked to estimate their adherence using Likert-type questions (all, most, half, some, or none). At the SVR visit, participants will also be asked to indicate the percentage of study medication that they actually took on a visual analog scale. At the week 4 remote contact assessment and week 24/SVR evaluation visit, participants who report less than perfect adherence will be asked about barriers to adherence.

Health Outcomes Questionnaire (EQ-5D)

The EQ-5D is a validated instrument used to collect data about quality of life (<http://www.euroqol.org>). The instrument asks questions and each has three possible responses (EQ5D-3L version). The instrument asks respondents to comment on their degree of mobility, self-care, usual activities, pain/discomfort, and anxiety/depression, and then ask participants to record their current health-related quality of life state using a vertical visual analogue scale (0-100 range). The instrument has been translated into a variety of languages and is available as a paper form, a computer-based form, a tablet/cell phone form, or as an interview.

Responses must be recorded on an eCRF from the entry visit and week 24/SVR evaluation, and weeks 48 and 72 visits. In addition, responses must be recorded in the event of an unplanned study visit.

Health Care Utilization Questionnaire

The health care utilization questionnaire solicits participant-reported health care utilization in the past 4 weeks including: 1) nights spent in a hospital bed, 2) visits to an emergency department, and 3) visits to a doctor's office. This questionnaire will be administered during visits at entry, week 24/SVR evaluation, and weeks 48, 72, and any unplanned visits. Responses must be recorded on an eCRF.

Substance Use Questionnaire

The substance use questionnaire will be administered at entry, week 24/SVR evaluation and weeks 48 and 72 visits. The Alcohol, Smoking and Substance Involvement Screening Test (ASSIST) survey that was developed for the WHO by an international group of researchers and clinicians as a technical tool to assist with early identification of substance use-related health risks and substance use disorders will be used. This tool has been validated globally and captures information on alcohol, smoking, and injection and non-injection drug use.

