12.0 COST-BENEFIT ANALYSIS PLAN

The cost-benefit analysis will employ the resource utilization data collected at planned/unplanned study visits until the SVR is assessed (week 24/SVR evaluation visit) as well as SVR data and utilization data to develop an estimate of cost/SVR attained.

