12.3 General Approach to Costing

The cost/SVR attained will be assessed from two perspectives.

12.3.1 The perspective of the clinic/program/site treating the participant (program perspective). These costs include the cost of staff, laboratory monitoring, and medications involved in delivering HCV treatment to a participant. These costs begin at week 0 and continue through the week 24/SVR evaluation. The program cost perspective is helpful to those who administer a clinic or treatment program who want to understand how MINMON would impact their program budget.

There are two cost components from the program perspective:

1. Cost of HCV medications
2. Cost of planned and unplanned study visit evaluations between week 0 and the week 24/SVR evaluation visit

12.3.2 The healthcare sector perspective—the health sector perspective is broader than the program perspective. It includes the costs of staff, laboratory monitoring and medications between weeks 0 and 24, the cost of healthcare

utilization outside of the study site between weeks 0 and 24, and any changes in utilization that may occur in the future as the result of the participant attaining SVR.

There are four cost components from the healthcare sector perspective:

1. Cost of HCV medications
2. Cost of planned and unplanned study visit evaluations between week 0 and the week 24/SVR evaluation visit
3. Cost of healthcare utilization outside of study sites between week 0 and the week 24/SVR evaluation visit
4. Cost saving (or additional cost) that may accrue because a person attains SVR and subsequently uses fewer (or more) healthcare resources. This cost saving (cost) is defined as the DIFFERENCE in healthcare utilization per month measured at the week 48 visit compared to the week 0 visit. The healthcare utilization questionnaire measures utilization over a 4-week recall period. This is defined as healthcare utilization per month. The difference in healthcare utilization per month between the week 48 assessment and the week 0 assessment is the monthly savings (or cost) attributable to attaining SVR. It will be assumed that the monthly savings (cost) applies to every month between week 24 and week 72.

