In addition, because this estimate of cost savings is uncertain, sensitivity analyses will be used to explore different estimates of saving attained including: 1) difference in utilization measured at the week 72 visit and the week 0 visit, 2) difference in utilization measured at week 72 and week 48 visits. In both of these sensitivity analyses, it will be assumed that the monthly savings (or cost) we estimate applies to every month between weeks 24 and 72.

Measures of utilization will be translated to cost (expressed in currency rather than units of resources consumed) using WHO CHOICE country-specific unit costs (http://www.who.int/choice/cost-effectiveness/inputs/health_service/en/).

It will be assumed that all resource utilization between weeks 0 and 24 is related to HCV medications. As a result, the cost estimate will tend to be biased toward a higher cost/SVR attained.

The primary analysis will be conducted in an intention to treat framework, whereby participants who are LTFU and do not return for the week 24/SVR evaluation visit are assumed to be treatment failures and not counted as "SVR" in the cost/SVR attained calculation. This approach will also tend to bias results to a higher cost/SVR attained. A sensitivity analysis will explore cost/SVR when it is assumed that the rate of SVR among those lost to follow-up at week 24 is similar to the SVR rate among those with week 24 confirmation of cure.

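### Healthcare-sector cost per SVR counts outside care from week 0 to the SVR visit, but the 4-week recall form reaches none of the 12 treatment weeks unless there is an unplanned visit

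*Protocol*

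**What the plan says.** Objective 1.4.5 (exploratory) is the cost per person cured. Protocol 12.0 bases it on "resource utilization data collected at planned/unplanned study visits until the SVR is assessed". The healthcare-sector perspective in 12.3.2 has four components. The third is "Cost of healthcare utilization outside of study sites between week 0 and the week 24/SVR evaluation visit", and 12.6.2 repeats it.

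The instrument is described in 6.3.15: "The health care utilization questionnaire solicits participant-reported health care utilization in the past 4 weeks". It asks about hospital nights, emergency department visits and doctor's office visits. Sections 6.3.15 and 12.4.3 give the same administration times: entry, week 24/SVR, weeks 48 and 72, and any unplanned visit.

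The fourth component is the saving after SVR, taken as week 48 use minus week 0 use. For it, 12.3.2 says: "The healthcare utilization questionnaire measures utilization over a 4-week recall period. This is defined as healthcare utilization per month". It adds: "It will be assumed that the monthly savings (cost) applies to every month between week 24 and week 72". Because this saving is uncertain, 12.3 offers two alternative contrasts: week 72 against week 0, and the "difference in utilization measured at week 72 and week 48 visits".

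Section 12.3 also attributes all use in weeks 0 to 24 to HCV medication and comments: "As a result, the cost estimate will tend to be biased toward a higher cost/SVR attained".

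**The concern.** The costed interval starts at the first dose, but the form looks back only 4 weeks from visits that, by design, do not fall in the treatment period. Under minimal monitoring no clinic visit is planned between entry and week 24 (Protocol 3.0), so the form misses the weeks in which scheduled contact has been removed. Whether participants then seek care elsewhere is what the healthcare-sector perspective adds to the program perspective. A cost per SVR reported as covering outside care from week 0 would rest mostly on weeks that the form did not ask about, while the text mentions only upward biases.

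The second issue sits in the savings component. One of the two sensitivity contrasts compares two visits that both follow SVR in participants evaluated on time, so it lacks the before-treatment value that a saving needs.

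**Working it through.** The documents state no coverage figure for this component, so there is none to reproduce. The check is interval overlap.

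**Inputs.** Treatment runs over weeks 0 to 12 (5.1.2). Recall is 4 weeks (6.3.15, 12.3.2). The week 24 visit window is weeks 22 to 28, and a missed visit can be made up to week 72 (6.2.4). Unplanned visits end at week 22 (6.2.6).

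**Coverage by the form, no unplanned visit.** The entry form covers weeks -4 to 0, so no treatment weeks. A form at week v covers weeks v-4 to v, which is 4/v of the costed interval.

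| SVR visit (week v) | Weeks recalled | Treatment weeks covered | Share of week 0 to v |
|---|---|---|---|
| 22 | 18-22 | 0 of 12 | 4/22 = 18.2% |
| 24 | 20-24 | 0 of 12 | 4/24 = 16.7% |
| 28 | 24-28 | 0 of 12 | 4/28 = 14.3% |
| 48 | 44-48 | 0 of 12 | 4/48 = 8.3% |

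Even the earliest visit opens its recall at week 18, which is 18 - 12 = 6 weeks after the planned end of treatment.

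**Unplanned visits.** One in weeks 4 to 12 adds 4 of 12 treatment weeks (33.3%). One at week 14 adds 2, and one at week 16 or later adds none. Covering all 12 would take 12/4 = 3 visits, at weeks 4, 8 and 12. These visits are meant for toxicities that cannot be settled by telephone (6.2.6), so the added coverage depends on symptoms.

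**Other sources.** The planned week 4 contact records adherence and locator updates and is not designed to assess AEs (6.3.22). At the SVR visit, 7.2 collects reportable AEs over the prior 24 weeks, and inpatient hospitalization is an SAE criterion.

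**If the 4-week count is not scaled.** With constant use, a week 24 visit captures 4/24 = 1/6 of use in weeks 0 to 24, an undercount.

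**If it is scaled to the interval.** The estimate is unbiased only if mean use over the whole interval equals mean use in the 4 recalled weeks. To show the size, assume constant post-treatment weekly use p and on-treatment use rp. The estimate is vp and the truth is 12rp + (v-12)p, so

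estimate/true = v / (12r + v - 12).

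The documents give no r; 0.5 to 2 is an assumed range.

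- v = 24: r = 0.5 gives 24/18 = 1.33; r = 1 gives 1.00; r = 2 gives 24/36 = 0.67.
- v = 28: r = 0.5 gives 28/22 = 1.27; r = 2 gives 28/40 = 0.70.

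**Savings contrasts.** Let monthly use be u at week 0 and u - s in every month of weeks 24 to 72, as 12.3.2 assumes.

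- Week 48 minus week 0: (u - s) - u = -s.
- Week 72 minus week 0: (u - s) - u = -s.
- Week 72 minus week 48: (u - s) - (u - s) = 0 for every s.

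If the saving is not constant, say a at week 48 and b at week 72, the last contrast equals a - b. That is only the change between two post-SVR visits.

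**The case against.** The overlap arithmetic is not in dispute. The best points on the other side are these.

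- **Some on-treatment care is recorded elsewhere.** This stands. A reader might infer that on-treatment outside care is wholly unobserved, but the documents do not support that: the AE collection in 7.2 may identify on-treatment admissions as SAEs. It would still miss emergency and doctor visits not tied to a reportable AE, and section 12 does not name it as a cost source.
- **The scaled range describes an estimator that the plan does not specify.** This stands as a limit. The per-month definition belongs to component 4, and no rule is given for component 3. The range also needs constant post-treatment use, because weeks 12 to 20 are unseen too at a week 24 visit. Hence both branches are shown. SAP 2.1 and 3.3 leave analyses outside the primary report to separate plans, which were not available here. Such a plan can choose a scaling rule but cannot recover weeks that were not asked about.
- **Week 72 minus week 48 need not be zero.** Correct if use changes between those visits. The contrast then measures that change, which is still not the saving relative to before treatment.
- **The stakes are small.** Agreed. This is an exploratory objective with two perspectives, only one of which uses the form. Unplanned site visits are costed separately under component 2, and there is no control arm (12.6).

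**Conclusion.** The gap is real and follows from the protocol's own text. Without an unplanned visit the form covers 0 of 12 treatment weeks, and between 14.3% and 18.2% of the costed interval for SVR visits within weeks 22 to 28.

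The effect on cost depends on a rule that the plan does not state. Unscaled, outside use is undercounted, to about one sixth at week 24 if use is constant, which runs against the upward bias in 12.3. Scaled, the direction is unknown: the range of 1.33 to 0.67 at week 24 rests on constant post-treatment use and an assumed 0.5 to 2 ratio. A reader might infer a known direction of bias in the final figure; the documents do not settle one. The other upward bias that 12.3 mentions, from counting participants lost to follow-up as failures ("This approach will also tend to bias results to a higher cost/SVR attained"), is not affected.

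Week 72 minus week 48 cannot serve as an estimate of savings from SVR in participants evaluated on time. This is a minor point overall: SVR, SAE and program-perspective results do not depend on it.

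**What to change.** **If week 24/SVR visits are still to come:** add three items to that visit's form asking for hospital nights, emergency visits and doctor visits since entry. Keep the 4-week items for the week 48 against week 0 contrast. The cost is a slightly longer form; the downside is that longer recall is less accurate, most of all for late SVR visits.

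**If those visits are done** (likely, since the 2020 letters of amendment re-time only weeks 48 and 72, and SAP 5.1.2 already uses observed week 48 visit timing):

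- State a scaling rule that takes the 4-week rate to the interval from week 0 to the SVR visit, and say that the unobserved weeks are imputed.
- Show a sensitivity range for the ratio of on-treatment to post-treatment use.
- Use SAE records to identify on-treatment admissions. The documents do not say that nights are recorded there, and emergency and doctor visits would stay imputed.
- Beside the 12.3 statement on attributing all use in weeks 0 to 24, note that unobserved use could offset that upward bias.

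This costs analysis wording plus use of records already collected.

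**In either case:** keep week 72 minus week 0 as the sensitivity analysis for savings. Week 72 minus week 48 may be kept as a check that use is stable after SVR, but should not be presented as a saving.
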